#### 4.2. Pilot sites description

- Italy: In Italy the end-user partner will be recruited from the Geriatrics Operating Unit of IRCCS INRCA. The research team includes multidisciplinary professional personnel that will have the possibility to meet end-users and their families to present the project and the modalities of possible participation. It will be responsibility of the research group to give technical support with the use of the TransCare technological ecosystem and take track of clinical flux of data acquired from each participant to correctly archive it and analyze it afterwards. End-users involved in pilot trial will first be screened by the appropriate physician or nurse for evaluation of clinical and physical/cognitive inclusion criteria and eventual recruitment for the TransCare project. The typical inpatient that is hospitalized in the IRCCS INRCA geriatrics department is an older adult, frail and often multi-morbid, who access the hospital for a series of conditions that fall in the acute infectious processes (urinary, biliary tract infection etc.) or cardiac sphere (chronic heart failure).
- Norway: In Norway, patients will be recruited from the municipal care services in collaboration with the local hospital (Sørlandet sykehus avd. Flekkefjord). The municipal services office serves as the single point of contact for all patients and is notified by the hospital of all potential new patients shortly after admission. The project multidisciplinary team will work closely with the municipal services office to identify and recruit patients. When a potential patient is identified, the project multidisciplinary team will meet the patient and their family to present the project. Screening for cognitive and physical inclusion criteria will be a shared responsibility between the hospital and municipal multidisciplinary teams. Home health services will provide technical training on the equipment to the patient and will also be responsible for the daily follow-up. Home health will respond to measurements and forms that trigger alarms. The typical patient receiving care in the FAR municipality is an older, frail patient with chronic illness, infections, or those requiring postoperative rehabilitation.

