The system allows the operator to only visualize if the technology is functioning and not to give an interpretation of the clinical data or send emergency alert of any kind. The system allows only the monitoring and the data collection of trends to understand the behavior and the disease trajectories over time and not real time/continuously. This is essential for research and patient data collection purposes, improving scientific knowledge on re-hospitalization and facilitating patient self-management. Thus, it is not the role of the operator to continuously monitor the data flowing through the platform, nor is it the role of the operator to promptly alert territorial health continuity services in case of emergency situations. Should the patient or his/her caregiver detect, by direct measurement or visualization on the platform, physiological parameters that may be suspect and indicators of dangerous situation, with or without the presence of symptomatology, then the patient or caregiver will be required to act as he or she would normally do, that is, to alert the appropriate medical authorities or general practitioner.

The administrator role is responsible for managing the account structure, users and devices. This role does not have access to any patient data.

Figure 4 Remote Patient Monitoring overview

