### 5.1. Technical description of medical devices

Medical devices adopted in the experimentation are in charge of acquiring biomedical parameters of the patient relevant to describe clinical condition of discharged patient.

All the patients recruited in this study will be given an established set of devices according to the specific pathology requirement and willingness to use. One exception is the Tanita RD-454 HR Smart Scale device, which will not be directly provided to users, but will be used at every assessment performed by health care personnel in the hospital. Table 2 reports the complete list of medical devices that will be provided to the participants and agreed among end-user partners. It is reported the complete list of all devices included in the international trial, but each end-user partner will adopt one or more devices depending on clinical need and potential use. Detailed information can be retrieved from Sec. 4 of D2.1.

In addition to the devices listed in the Table 2, the Norwegian pilot will use, only for certain patients, a system already integrated into the Tellu Platform that involves camera supervision equipment and personal alarms to enhance safety and support independent living. Camera supervision allows caregivers to remotely monitor individuals, ensuring their well-being while respecting privacy. Personal alarms provide users with a quick way to call for help in emergencies, offering peace of mind through features like GPS tracking and two-way communication. However, these two additional devices will not be adopted by the other partners and remain a feature exclusive to Norway.

Name	Туре	Description	Main functionalities
A&D Medical UC-352BLE scale	Medical device (CE)	Smart scale	A weight scale with Bluetooth connectivity. This scale is easy to use – the user stands on the scale until a value is shown on the display, and the measurement (Kg) is automatically transferred to the gateway.

State State			
Tanita RD-454 HR Smart Scale			
	Medical Device (CE)	Smart scale	Device to analyze different body compositions, including body water
A&D Medical UA-651 BLE or UA-656 BLE			
blood pressure meters	Medical device (CE)	Blood pressure meter	Ine cuff is fastened on the arm and the button is pressed on the device to start the measurement. The display shows the status, and the measurement is automatically transferred to the gateway when ready. Parameters acquired: Systolic pressure (mmHg), diastolic pressure (mmHg) and pulse (/min).

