the specific needs of each type of user. The Dialogg mobile application allows patients to interact with the system, recording measurements and communicating with healthcare professionals. Healthcare providers, on the other hand, use a dedicated web interface to monitor clinical parameters, manage alerts and update care plans. Platform administration is provided by specific tools for user, device and data security management. On the sensitive information protection front, an advanced authentication and security system based on OpenID Connect and OAuth 2.0 is implemented, with strict role management and an encryption system that complies with international ISO 27001 standards and European GDPR regulations. Every transaction is recorded in an audit log to ensure traceability and transparency in data access. A distinctive feature of the platform is its ability to integrate certified medical devices and physical activity tracking systems. With Bluetooth device compatibility, the system captures vital data such as blood pressure, blood glucose, body temperature, and oxygen saturation. In parallel, integration with Fitbit allows monitoring of parameters related to physical activity and sleep quality, providing a complete picture of the patient's health status. The collected data are transmitted and stored in the FHIR database, used for advanced processing based on machine learning, thus enabling timely intervention in case of abnormalities. Further adding value to the platform is its integration with Memas, a digital assistant designed to support patients in the daily management of their health. Through interactive tools, Memas provides educational materials, general suggestions on diet and exercise, as a "disease literacy" information system. No coaching intervention are meant to be performed with the platform.

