- Data collected by the researchers: The first step of the data analysis will deal with the description of • the sample. Continuous variables will be reported as either mean and standard deviation or median and interquartile range based on their distribution (assessed using Kolmogorov-Smirnov test). Categorical variables will be expressed as an absolute number and percentage. Comparison of baseline measurements between groups will be evaluated by unpaired t-test (for normal distribution), Mann-Whitney U tests (for non-normal distribution), or Chi-Square tests (for categorical variables). Within each group, independent and dependent variables will be compared between the pre- and post- conditions using the same tests as appropriate. The treatment effect on the outcome variables will be evaluated by using repeated measures ANOVA, to compare the changes over time in the outcome measures between the intervention group and the control group. Moreover, a linear regression model on the outcome variation between baseline and follow-up will be estimated to evaluate the effect of the treatment adjusted for all potential confounders. Descriptive statistical analyses will be performed on the quantitative data with SPSS or Rstudio. All data acquired in the trial will be analysed directly by the research centres involved in the project consortium. Monitored data will be used as input to the ML-based post discharge analytics for training and inference processes allowing for the prediction of different parameters among patients involved in the experimentation. The ML component will determine insights that can be used as support by medical professionals to identify the problems that require proactive intervention. Work will be done on anonymized data and not on personal data, and the AI model will not interact for the testing phase with the end user, be it the patient or the practitioner. The practitioners can only access the results of the ML inference for their remotely monitored patients and to visualize the results in order to support their decisions regarding patients' treatment.

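### The protocol contradicts itself on who sees and acts on monitored data and machine-learning output, so a pooled effect cannot be credited to self-management or to one defined intervention

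*Protocol*

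**What the plan says.** **Monitored data.** Section 5 (Equipment) is written for the whole trial. It says: "The system allows the operator to only visualize if the technology is functioning and not to give an interpretation of the clinical data". It also rules out emergency alerts from the system and describes the data collection as neither real-time nor continuous. When a value looks suspect, "the patient or caregiver will be required to act as he or she would normally do".

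Section 4.2 gives Norwegian home health services the daily follow-up and adds: "Home health will respond to measurements and forms that trigger alarms". For Italy and Romania, the same section describes technical support, tracking of data and archiving. It mentions no response to values.

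Section 5.3, with no country named, says that healthcare providers "use a dedicated web interface to monitor clinical parameters, manage alerts and update care plans". It also says that machine-learning processing makes prompt action on abnormal values possible.

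**Machine-learning output.** Section 9 says that "the AI model will not interact for the testing phase with the end user, be it the patient or the practitioner". The next sentence reads "The practitioners can only access the results of the ML inference for their remotely monitored patients" and goes on to give the purpose as support for treatment decisions.

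**Uniformity.** Section 8.1 opens by stating that recruitment and experimentation do not differ between the three pilot sites. Section 5.1 says that "the Norwegian pilot will use, only for certain patients, a system already integrated into the Tellu Platform", meaning camera supervision and personal alarms, and declares this a Norwegian feature.

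**Mechanism.** Section 6.1 defines the primary endpoint as a lower 30-day rehospitalization rate achieved by supporting patients' self-management.

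**The concern.** Self-monitoring in which only the patient or caregiver reacts is a different intervention from monitoring in which a care service answers alarms or a practitioner uses model output. The protocol describes both and calls the procedures uniform.

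Two things are at stake. The first is interpretation: section 6.1 names self-management as the route to benefit, and a benefit that came through Norwegian alarm response would be reported under that name. The second is conduct: staff who read section 5 and staff who read section 4.2 or 5.3 will reach different conclusions on whether an abnormal reading is to be acted on.

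Power is a further issue, because the sample size assumes one common effect across sites that may not be delivering the same thing.

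**Working it through.** **1. Statements side by side**

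| Question | One statement | The other |
|---|---|---|
| Does staff act on readings? | Section 5: no interpretation by the operator, no emergency alert; patient or caregiver acts as usual | Section 4.2 (Norway): home health answers alarms. Section 5.3 (no country): providers manage alerts and change care plans |
| Does ML output reach practitioners? | Section 9: no contact with patient or practitioner in testing | Section 9, next sentence: practitioners view it for their own patients |
| Same procedures at all sites? | Section 8.1: yes | Section 4.2: a response is described for Norway only |

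The operator of section 5 and the provider of section 5.3 may be different roles, since section 5 mentions role-specific interfaces. The protocol does not define one against the other, and section 5 assigns the reaction to the patient or caregiver. A split of roles therefore does not settle sections 5 and 4.2, and it has no bearing on the two sentences of section 9.

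**2. Inputs**
- Table 1, cases/controls: Italy 50/50, Romania 15/15, Norway 40/40.
- Section 9: 19.3% control, 5.2% intervention, two-sided Fisher's exact test, alpha 0.05, power 0.85, 103 per arm.
- Section 7: 105 per arm planned.

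**3. The plan's own figure.** Exact power of Fisher's test, summed over both binomial distributions, is 0.849 at 102 per arm and 0.852 at 103 per arm. The stated 206 is reproduced. At 105 per arm, power is 0.860.

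**4. Effect of unequal delivery (assumption).** Let Norway have the full 14.1 points and let Italy and Romania keep a fraction f of it, with 19.3% in every control group. Norway's share is 40/105 = 38.1% and the rest is 65/105 = 61.9%.

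Pooled difference = 14.1 × (0.381 + 0.619 f)

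| f | Pooled difference (points) | Intervention rate | Power, 105 per arm |
|---|---|---|---|
| 1 | 14.1 | 5.2% | 0.86 |
| 0.75 | 11.9 | 7.4% | 0.67 |
| 0.50 | 9.7 | 9.6% | 0.45 |
| 0.25 | 7.5 | 11.8% | 0.26 |
| 0 | 5.4 | 13.9% | 0.14 |

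The documents give no value for f.

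**5. Could a test by country sort this out?** Take the extreme case f = 0 and compare the risk difference in Norway with that elsewhere.
- Variance, Norway: (0.193 × 0.807 + 0.052 × 0.948)/40 = 0.00513
- Variance, elsewhere: 2 × 0.193 × 0.807/65 = 0.00479
- SE = √0.00992 = 0.0996; z = 0.141/0.0996 = 1.42; power is about 29%

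In Romania, 15 experimental participants at 5.2% have no event with probability 0.948^15 = 0.45, so a logistic interaction term might not be estimable. For the full 14.1 points, Norway alone (40 per arm) has power 0.36.

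**The case against.** Much of the variation between countries is declared. Section 1 says that implementation will be adapted to context, section 5.1 lets each partner choose devices and confines cameras and personal alarms to Norway, and section 5.2 allows different trackers. That stands: the device differences are an acknowledged design choice. None of these sections, however, says that one country answers alarms and the others do not.

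Section 5.3 can be read as a description of what the platform is able to do, with the provider a different role from the operator. That weakens the conflict between sections 5 and 5.3. It leaves those between sections 5 and 4.2 and within section 9.

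Section 5 bars emergency alerts. A reader might take it to bar every alert, but the text does not go that far, and non-urgent follow-up could coexist with it.

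A reader might also infer that the pooled comparison is invalid or cannot be attributed to anything. The documents do not support this. Table 1 plans equal numbers of cases and controls in each country, so the contrast between arms still estimates an average effect of the package as delivered, and section 3.1 does speak of a new care pathway.

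A clean division into 40 participants with a response and 65 without is likewise not established, because section 5.3 names no country.

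The consent material is not available here, so nothing can be said on whether participants receive conflicting information. Section 10 does say that they will be told the limits of the technology.

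**Conclusion.** The contradictions are in the current text and prevent the protocol from being followed as written. They concern who responds to readings (section 5 against sections 4.2 and 5.3), whether practitioners see model output (two adjacent sentences of section 9), and the claim of uniform procedures (section 8.1).

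For the statistics, the consequence is one of interpretation: a pooled result is the average effect of a mixed package and should not be reported as a self-management effect or as the effect of one defined intervention. Norway, the only country with a described alarm response, makes up 38% of the experimental arm.

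The loss of power runs from none to severe (0.86 down to 0.14), depending wholly on an assumed fraction of effect at the other sites. The lowest figure is the extreme case, not an expectation. A test of arm by country cannot carry the interpretation, since it would have only about 29% power even in that extreme.

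**What to change.** 1. Reconcile sections 4.2, 5, 5.3, 8.1 and 9 into one statement per country: who sees the readings, who sees the machine-learning output, and what follows. Define operator and healthcare provider against each other. Which rule applies is for the sponsor and investigators to decide.
2. Check that the participant information matches that statement.
3. Record contacts triggered by monitored data, as part of the description of the intervention delivered.
4. Adjust the primary comparison for country. Report country-specific risk differences with confidence intervals as descriptive only, and do not rely on an arm-by-country test. If a separate SAP already provides for this, it need only be kept consistent.
5. Describe the primary result as the effect of the package as delivered.

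**Cost.** The changes are mostly wording, but the trial was submitted to ethics committees in each partner country, so notification may be needed in three places. Recording contacts adds some work, chiefly for Norwegian home health. Country-specific intervals will be wide, above all in Romania with 15 per arm.

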### 5.1. Technical description of medical devices

Medical devices adopted in the experimentation are in charge of acquiring biomedical parameters of the patient relevant to describe clinical condition of discharged patient.

All the patients recruited in this study will be given an established set of devices according to the specific pathology requirement and willingness to use. One exception is the Tanita RD-454 HR Smart Scale device, which will not be directly provided to users, but will be used at every assessment performed by health care personnel in the hospital. Table 2 reports the complete list of medical devices that will be provided to the participants and agreed among end-user partners. It is reported the complete list of all devices included in the international trial, but each end-user partner will adopt one or more devices depending on clinical need and potential use. Detailed information can be retrieved from Sec. 4 of D2.1.

In addition to the devices listed in the Table 2, the Norwegian pilot will use, only for certain patients, a system already integrated into the Tellu Platform that involves camera supervision equipment and personal alarms to enhance safety and support independent living. Camera supervision allows caregivers to remotely monitor individuals, ensuring their well-being while respecting privacy. Personal alarms provide users with a quick way to call for help in emergencies, offering peace of mind through features like GPS tracking and two-way communication. However, these two additional devices will not be adopted by the other partners and remain a feature exclusive to Norway.

Name	Туре	Description	Main functionalities
A&D Medical UC-352BLE scale	Medical device (CE)	Smart scale	A weight scale with Bluetooth connectivity. This scale is easy to use – the user stands on the scale until a value is shown on the display, and the measurement (Kg) is automatically transferred to the gateway.

State State			
Tanita RD-454 HR Smart Scale			
	Medical Device (CE)	Smart scale	Device to analyze different body compositions, including body water
A&D Medical UA-651 BLE or UA-656 BLE			
blood pressure meters	Medical device (CE)	Blood pressure meter	Ine cuff is fastened on the arm and the button is pressed on the device to start the measurement. The display shows the status, and the measurement is automatically transferred to the gateway when ready. Parameters acquired: Systolic pressure (mmHg), diastolic pressure (mmHg) and pulse (/min).
Contour Next ONE glucometer			
· · · · · · · · · · · · · · · · · · ·	Medical device (CE)	Glucometer	Device able to acquire blood glucose level (mmol/L)
Nonin Pulse Oximeter	Medical device (CE)	Pulse oximeter	It starts measuring as soon as a finger is correctly inserted. Spot Check measurement is abled, meaning the device gives one measurement once the value is stable. The device also supports continuous measurement. Parameter acquired: Oxygen saturation (%) and pulse (/min)
A&D Medical UT-201BLE Thermometer			
Contraction of the second seco	Medical device (CE)	Thermometer	Device able to measure body temperature (°C). Turned on with the power button and positioned to make the measurement. It beeps when it has a temperature reading, and transfers to the app.
OMRON Complete			
	Medical device (CE)	Blood pressure meter + ECG	Device to monitor blood pressure and heart rate. It also has the function of performing a single-lead ECG.

# 5.2. Technical description of non-medical devices

An activity tracker provides valuable insights into activity, sleep, and general health, offering extensive data from a single device. However, these devices are not medically certified or diagnostic tools, and their measurements, such as heart rate and body temperature, are less accurate than specialized sensors. Despite this, they excel at identifying trends, especially activity levels, which are crucial for target patients in this project. Moreover, they can continuously generate substantial data for scientific analysis. Access can be difficult, as data is typically processed and stored in closed systems, requiring careful consideration when choosing and integrating these devices into TransCare. Table 3 reports a summary of main functionality of the selected device. However, it is not necessary that all end-user partners adopt the same model of the device, but it is important that features (collected parameters) are the same. Further details about activity tracking technology description and integration can be found in Sec.5 of D2.1.

Table 3 Activity tracking smart band description

Name	Туре	Description	Main functionalities
Fitbit	Commercial non- medical device (CE)	Activity tracking smart band	Main tracking functionalities: Heart rate tracking, resting heart rate, steps, distance, calories, sleep tracking stages, blood oxygen tracking, breathing rate, skin temperature variation.

Furthermore, participants and caregivers will be given a tablet where they can use and navigate the platform, as reported in Table 4. Alternatively, participants can download the app to their own device.

